Title of Study:	A Double-Masked, Randomized, Controlled, Multiple-Dose Study to Evaluate the Efficacy, Safety and Tolerability of QR-421a in Subjects with Retinitis Pigmentosa (RP) due to Mutations in Exon 13 of the USH2A Gene with Early to Moderate Vision Loss		
Phase of Development:	Phase 2/3		
Study Period:	Anticipated to be approx	ximately 34 months	
Duration of Subject Participation:	Approximately 27 months (up to 12 weeks screening; 24 months treatment)		
Rationale:	There are currently no approved therapies for the treatment of RP due to mutations in exon 13 of the USH2A gene and disease management is supportive; therefore, a large unmet medical need exists in this sight-threatening condition. Study PQ-421a-004 will investigate the efficacy and safety of 2 dose regimens of QR-421a in subjects with early to moderate vision loss.		
Objectives: Primary To evaluate the efficacy of	Primary ● To evaluate the efficacy of QR-421a Primary endp • Change from the control of the		n mean sensitivity (based on nonths of treatment versus
		sham-procedure	

Page 4 of 67 29 October 2021 **ProQR Therapeutics**

Secondary Key Secondary endpoints To further evaluate efficacy of QR-421a Ellipzoid Zone area (EZ) as measured by Spectral Domain optical coherence tomography SD-OCT To evaluate the safety and tolerability of QR-421a Other Secondary endpoints To evaluate changes in Patient-Reported Outcome Change from baseline in the following outcome (PRO) measures in subjects treated with QR-421a measures: To evaluate systemic exposure of QR-421a **BCVA** 0 Spectral domain optical coherence tomography (SD-OCT) (other measures) Low Luminance Visual Acuity (LLVA) Other measures of static perimetry Full-field Stimulus Threshold (FST) Change from baseline in PRO measures, as assessed Michigan Retinal Degeneration Questionnaire (MRDQ) (Lacy 2021) Patient Global Impressions of Severity (PGI-S) Patient Global Impressions of Change (PGI-C) Ocular and non-ocular adverse events (AEs) Exposure of QR-421a in serum **Exploratory Exploratory endpoints** To evaluate the effects of QR-421a on mobility course Change from baseline in mobility course score performance

Number of Subjects (planned):	Approximately 120 subjects		
Study Design	PQ-421a-004 is a double-masked, randomized, controlled, multiple-dose study to evaluate the efficacy, safety and tolerability of QR-421a in subjects with RP due to mutations in exon 13 of the USH2A gene with early to moderate vision loss.		
	At study start subjects will be randomized to one of the following treatment groups:		
	 Group 1: QR-421a 180/60 μg (180 μg loading dose administered on Day 1, 60 μg maintenance dose administered at Month 3 and every 6 months thereafter; n = 40) 		
	 Group 2: QR-421a 60/60 μg (60 μg loading dose administered on Day 1, 60 μg maintenance dose administered at Month 3 and every 6 months thereafter; n = 40) 		
	3) Group 3: Sham-procedure (administered on Day 1, Month 3 and every 6 months thereafter; n = 40)		
	The primary endpoint will be assessed at 12 months of treatment. Analysis of all other efficacy and safety parameters will also be reported at that time point. All efficacy and safety parameters will continue to be followed during the 24-month treatment period.		

ProQR Therapeutics Page 5 of 67

Study Plan

The study includes screening period of up to 12 weeks.

During the screening period, subjects will be assessed according to the eligibility criteria.

It is

recommended that screening will be conducted in a stepwise manner, so that eligibility is confirmed first with less intensive assessments and more intensive assessments are conducted after eligibility by all other criteria have been confirmed.

Subjects who meet all eligibility criteria will be enrolled into the study and will receive their dose of study treatment on Day 1. QR-421a will be administered via intravitreal (IVT) injection into the subject's study eye (ie, the first eye to be treated, see section 4.2.1.2 for selection of the study eye) in accordance with the procedures outlined in the Study Reference Manual. Subjects receiving the shamprocedure will undergo a procedure that will closely mimic the active injection, but there will be no penetration of the globe. Administration of study treatment, as well as clinical monitoring of the subject during and right after administration of study treatment, will be performed by an unmasked physician. All other clinical assessments will be performed by a separate, masked physician, or by masked study personnel.

After each administration of study treatment subjects will be monitored clinically for safety, including intraocular pressure (IOP) and signs of inflammation.

Frequent study visits and safety monitoring by the Investigator will be in place, together with oversight by the Medical Monitor and the Data Monitoring Committee (DMC) (see Section 9.1). The Investigator or the Medical Monitor (in consultation with the DMC) may decide to hold (delay or skip) or discontinue study treatment for an individual subject. Stopping criteria are described in Section 4.2.2. Subjects who discontinue study treatment will continue to be followed for safety and efficacy.

Efficacy and safety assessments, including retinal structure changes and functional assessments of vision and patient-reported outcome (PRO) measures will be performed at selected study visits as indicated in the Schedule of Events (SOE)

All assessments will be performed on both eyes. A central reading center will grade structural and functional exams in a masked way. Any assessment may be repeated if the results are considered unreliable or of unacceptable quality by the Investigator or the reading center.

Samples for systemic exposure analysis will be collected as indicated in the SOE

Assessments can be completed over multiple non-consecutive days.

Diagnosis and Main Criteria for Eligibility Relating to Study Initiation:

Inclusion Criteria Relating to Study Initiation:

The subject is eligible for the study and thus eligible to receive QR-421a or sham-procedure in the study eye if all the following inclusion criteria apply at Screening/Day 1:

 An adult (≥ 18 years) willing and able to provide informed consent for participation prior to performing any study related procedures, and suitable verbal, auditory, written and/or tactile sign language communication as to allow informed consent to be obtained, in the opinion of the Investigator.

OR

A minor (12 to < 18 years) with a parent or legal guardian willing and able to provide written permission for the subject's participation prior to performing

- any study related procedures and pediatric subjects able to provide age appropriate assent for study participation.
- 2. An adult willing to comply with the protocol, follow study instructions, attend study visits as required and willing and able to complete all study assessments.

OR

A minor able to complete all study assessments and comply with the protocol and has a parent or caregiver willing and able to follow study instructions, and attend study visits with the subject as required.

- 3. Clinical presentation consistent with RP with Usher syndrome type 2 or non-syndromic form of RP (NSRP), based on ophthalmic, audiologic, and vestibular examinations.
- 4. A molecular diagnosis of homozygosity or compound heterozygosity for 1 or more pathogenic exon 13 mutations in the *USH2A* gene, based on genetic analysis at screening.
- 5. BCVA better than ≥69 letters (approximate Snellen equivalent 20/40) in the study eye, using the best BCVA reading at Screening (see Section 8.1) and based on the Early Treatment Diabetic Retinopathy Study (ETDRS).
- 6. Impairment of Visual Field (VF) in the opinion of the Investigator as determined by perimetry, with a continuous area of central field greater than or equal to 10 degrees diameter in each meridian as measured by a size V4e target, and a mean defect of ≥ 10 dB,

-in the study eye.

- 7. Clearly visible and measurable ellipsoid zone (EZ) width and/or area on SD-OCT, per investigator judgement.
- 8. No limitations to SD-OCT image collection that would prevent high quality, reliable images from being obtained in both eyes, as determined by the Investigator.
- Reliable BCVA, perimetry, and other measurements in both eyes, as described in the Study Reference Manual and Imaging Manual and determined by the Investigator.
- 10. No visually significant ocular media opacities and adequate pupillary dilation to permit good quality retinal imaging, as assessed by the Investigator.

ProQR Therapeutics Page 7 of 67
29 October 2021

Exclusion Criteria Relating to Study Initiation:

The subject is ineligible for the study if any of the following criteria apply at Screening/Day 1:

- Presence of additional non-exon 13 USH2A pathogenic mutation(s) on the USH2A allele carrying the exon 13 mutation in subjects who have monoallelic exon-13 mutations.
- Presence of non-exon 13 USH2A pathogenic mutation(s) on both USH2A alleles in subjects who have biallelic exon 13 mutations.
- Presence of pathogenic mutations in genes (other than the *USH2A* gene) associated with Usher syndrome Type 2 or NSRP, or other inherited retinal degenerative diseases or syndromes.
 - Note: The confirmed presence of homozygous or compound heterozygous known disease-causing mutations in other genes involved in recessive retinal dystrophies (RD), or the confirmed presence of known disease-causing mutations in genes involved in dominant or X-linked retinal dystrophies is exclusionary.
- Presence of any significant ocular or non-ocular disease/disorder (or medication and/or laboratory test abnormalities) which, in the opinion of the Investigator and with concurrence of the Medical Monitor, may either put the subject at risk because of participation in the study, may influence the results of the study, or the subject's ability to participate in the study. This includes but is not limited to a subject who has uncontrolled cystoid macular edema (CME) in the study eye. CME is permissible if stable for 3 months (with or without treatment). Past CME is permissible if resolved for more than 1 month.
- History or presence of ocular herpetic diseases (including herpes simplex virus, varicella zoster or cytomegalovirus) in either eye.
- Presence of any active ocular infection in either eye.
- Presence of any of the following lens opacities in the study eye based on the age-related eye diseases study (AREDS) lens grading scale: cortical opacity ≥ +2, posterior subcapsular opacity $\geq +2$, or a nuclear sclerosis $\geq +2$, and which are: 1) clinically significant in the opinion of the Investigator, 2) would adequately prevent clinical and photographic evaluation of the retina.
- History of amblyopia in the study eye that resulted in significant vision loss, in the opinion of the Investigator.
- Receipt within 3 months prior to Screening of any intraocular or periocular surgery (including refractive surgery), or an IVT injection other or planned intraocular surgery or procedure during the course of the study.
- 10. Current treatment or treatment within the past 12 months with therapies known to influence the immune system (including but not limited to steroid implants, cytostatics, interferons, tumor necrosis factor (TNF)-binding proteins, drugs acting on immunophilins, or antibodies with known impact on the immune system). Subjects that have been treated with systemic steroids within the past 12 months or that require intermittent use of topical steroids may be considered for inclusion following approval by the Medical Monitor.
- 11. A history of glaucoma or an IOP greater than 24 mmHg in either eye that is not controlled with medication or surgery.
- 12. Use of any investigational drug or device within 90 days or 5 half-lives preceding the first dose of study medication, whichever is longer, or plans to participate in another study of an investigational drug or device during the course of the study.

	13. Any prior treatment with genetic or stem-cell therapy for ocular or non-ocular disease.		
	History of malignancy within 2 years prior to Screening, except adequately treated squamous or basal cell carcinoma of the skin or carcinoma in situ of the cervix that has been successfully treated. Known hypersensitivity to antisense oligonucleotides or any constituents of the injection. Pregnant and breastfeeding subjects. Females of childbearing potential and males must comply with using highly effective methods of contraception as defined in Section 6.2.2. Women of non-childbearing potential may be included without the use of adequate birth control, provided they meet the criteria in the protocol (see Section 6.2.2).		

ProQR Therapeutics
Page 9 of 67
29 October 2021

Study Drug, Dosage and Mode of Administration:	Two dose regimens will be tested: 1. 180 μg loading dose, 60 μg maintenance dose (180/60 μg) 2. 60 μg loading dose, 60 μg maintenance dose (60/60 μg)
Duration of Treatment:	24 months The Sponsor plans on providing access to study drug after the end of study (EOS) in an open-label extension study.
Reference Therapy, Dosage and Mode of Administration:	Sham procedure
Statistical Methods:	The primary endpoint for efficacy will be mean change from baseline in retinal sensitivity in a pre-specified area with at least 5 loci at Month 12 between QR-421a-treated and sham-treated eyes. Hypothesis testing of the mean treatment effect between QR-421a treatment and sham procedure will be performed using an ANCOVA model at a one-sided significance level of alpha=0.025. Since two QR-421a doses are being tested, Type I error will be controlled for multiplicity using appropriate methods.

ProQR Therapeutics

TABLE OF CONTENTS

CLIN	NICAL	STUDY 1	PROTOCOL	1
INVE	ESTIG	ATOR SI	GNATURE PAGE	2
PRO	TOCO	L APPRO	OVAL PAGE	3
1.0	SYN	OPSIS		4
TAB	LE OF	CONTE	NTS	11
LIST	OF FI	GURES.		15
LIST	OF A	BBREVIA	ATIONS AND DEFINITIONS OF TERMS	16
2.0	INT	RODUCT	ION	19
	2.1		s Pigmentosa	
	2.2		a for the Treatment of RP due to Mutations in Exon 13 of the USH.	
	2.3	Benefit	Risk Assessment.	21
	2.4	Study R	ationale	21
	2.5	Measur	es to Minimize Bias	21
	2.6	Dose Se	election	22
	2.7	Study P	opulation	23
3.0	STU	DY OBJE	CCTIVES	23
	3.1	Primary	Objective	23
	3.2	Seconda	ary Objective	23
	3.3	Explora	tory	24
4.0	STU	DY OVE	RVIEW	24
	4.1	Criteria	for Evaluation	24
		4.1.1	Primary Endpoints	24
		4.1.2	Secondary Endpoints	24
		4.1.3	Exploratory Endpoints	25
	4.2	Study D	Design	25

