4.1.1 Primary Endpoints

 Change from baseline in mean sensitivity (based on static perimetry) at 12 months of treatment versus sham-procedure

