4.1.2 Secondary Endpoints

The order in which the secondary endpoints will be analysed will be defined in the Statistical Analysis Plan (SAP).

Key Secondary Endpoint

• Ellipzoid Zone area (EZ) as measured by Spectral Domain optical coherence tomography SD-OCT

Other Secondary Endpoints

- Change from baseline in the following outcome measures:
 - o BCVA
 - Spectral domain optical coherence tomography (SD-OCT) (other measures)
 - Low Luminance Visual Acuity (LLVA)
 - Other measures of static perimetry
 - Full-field Stimulus Threshold (FST)
- Change from baseline in PRO measures, as assessed by:
 - Michigan Retinal Degeneration Questionnaire (MRDQ) (Lacy 2021)
 - o Patient Global Impressions of Severity (PGI-S)
 - o Patient Global Impressions of Change (PGI-C)
- Ocular and non-ocular adverse events (AEs)

Exposure of QR-421a in serum

4.1.3 **Exploratory Endpoints**

Change from baseline in mobility course score

4.2 **Study Design**

PQ-421a-004 is a double-masked, randomized, controlled, multiple-dose study to evaluate the efficacy, safety, and tolerability of QR-421a in subjects with RP due to mutations in exon 13 of the *USH2A* gene with early to moderate vision loss.

At study start subjects will be randomized to one of the following treatment groups:

- Group 1: QR-421a 180/60 µg (180 µg loading dose administered on Day 1, 60 µg maintenance dose administered at Month 3 and every 6 months thereafter; n = 40)
- Group 2: QR-421a 60/60 µg (60 µg loading dose administered on Day 1, 60 µg maintenance dose administered at Month 3 and every 6 months thereafter; n = 40)
- Group 3: Sham-procedure (administered on Day 1, Month 3 and every 6 months thereafter; n = 40)

The primary endpoint will be assessed at 12 months of treatment. Analysis of all other efficacy and safety parameters will also be reported at that time point. All efficacy and safety parameters will continue to be followed during the 24-month treatment period.

The same safety monitoring protocol and efficacy assessments will apply to both eyes.

ProQR Therapeutics Page 25 of 67

4.2.1 **Study Plan**

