2.2. Randomization Methodology

The randomization procedure used to assign study treatment to eligible subjects/eye was through a centralized Interactive Response Technology (IRT), utilizing the randomization schedule generated by the designated unmasked statistician.

Two periods of randomization were planned:

Subjects who satisfy all eligibility criteria at Day 1 were randomized in a 1:1:1 ratio to one of the following groups:

- ο Ultevursen 180/60 μg
- ο Ultevursen 60/60 μg
- Sham-procedure

The randomization in both periods has been stratified at Day 1 on one single factor, collected during the Day 1 visit: Syndromic subjects versus Non-Syndromic subjects.

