5. CHANGES TO PLANNED ANALYSES

As the study is prematurely stopped by Sponsor's decision, no formal statistical analysis will be produced. Only disposition, demographic and baseline characteristics, and overview of AEs will be summarized in tables. By-subjects data listings will be produced based on raw data.

6. **REFERENCES**

1. International Council on Harmonization, Statistical Principles for Clinical Trials (ICH E9)

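### Do the two wordings of the primary perimetry endpoint leave the tested quantity, and its 0.025 error rate, open?

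*Protocol*

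**What the plan says.** Section 4.1.1 of the protocol gives the primary endpoint as "Change from baseline in mean sensitivity (based on static perimetry) at 12 months of treatment versus sham-procedure". It does not say which loci enter the mean. The synopsis endpoint list also speaks of mean sensitivity, as far as its broken text can be read.

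The Statistical Methods entry of the synopsis is more specific: "mean change from baseline in retinal sensitivity in a pre-specified area with at least 5 loci at Month 12", compared between treated and sham eyes. The next sentence attaches the test to that quantity, an "ANCOVA model at a one-sided significance level of alpha=0.025". The entry then adds: "Since two QR-421a doses are being tested, Type I error will be controlled for multiplicity using appropriate methods".

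Section 4.1.2 ranks "Other measures of static perimetry" among the other secondary endpoints.

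The abbreviated SAP, written after the sponsor stopped the study, defines neither version. Section 5 states that "no formal statistical analysis will be produced". Section 4.7 lists static perimetry by subject and plans no perimetry summary or comparison.

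**The concern.** A mean over every tested locus and a mean over a chosen area are different variables. They carry different noise, and an effect confined to part of the retina shrinks when loci outside that part are averaged in. If the two protocol texts are rival definitions, the choice between them also decides which measure is primary and which falls to the secondary list. A sponsor holding both results could call the better one primary and cite the protocol for it. The promised multiplicity control concerns the two doses, so it would not cover that choice. In a Phase 2/3 trial with a formal one-sided test, that would matter.

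**Working it through.** **Comparing the wordings**

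| Element | Section 4.1.1 | Synopsis, Statistical Methods |
|---|---|---|
| Quantity | mean sensitivity, static perimetry | retinal sensitivity |
| Contrast | change from baseline, against sham | change from baseline, against sham |
| Time | 12 months | Month 12 |
| Loci averaged | not stated | an area fixed in advance, at least 5 loci |
| Test attached | none | one-sided ANCOVA, 0.025 |

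Only the loci differ, and there one text is silent while the other is specific. An average over the loci of a set area is still a mean sensitivity from static perimetry, so the texts are compatible. On that reading the secondary item covers whatever perimetry measures are not primary, and nothing changes rank.

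**The plan's own figures.** The level is a design choice: 0.05/2 = 0.025, critical value 1.960. The planned size, "Approximately 120 subjects", agrees with three arms of 40 "randomized in a 1:1:1 ratio": 3 × 40 = 120. It cannot be re-derived from power, because no effect size, standard deviation or power is visible.

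**Worst case for one dose against sham.** Suppose both measures are tested at 0.025 and the better one is reported. Under the null, with correlation ρ between the test statistics:

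error = P(max(Z1, Z2) > 1.960) = 2 × 0.025 − P(Z1 > 1.960 and Z2 > 1.960)

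At ρ = 0 this is 1 − (1 − 0.025)² = 0.0494. The ceiling is 2 × 0.025 = 0.05.

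**Worst case for two doses.** As an assumed example of dose adjustment, each dose is tested at 0.0125. The dose comparisons correlate at 40/(40 + 40) = 0.5 through the shared sham arm. With one fixed endpoint the familywise error is 0.0232. With a free choice between two measures (1,000,000 simulated draws) it is given in the last column.

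| ρ between measures (assumed) | One dose, better of two at 0.025 | Two doses at 0.0125 each, better of two |
|---|---|---|
| 0 | 0.0494 | 0.0461 |
| 0.3 | 0.0476 | 0.0446 |
| 0.5 | 0.0454 | 0.0428 |
| 0.7 | 0.0417 | 0.0393 |
| 0.8 | 0.0390 | 0.0368 |
| 0.9 | 0.0352 | 0.0333 |
| 0.95 | 0.0323 | 0.0307 |
| 1 | 0.0250 | 0.0233 |

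The documents give no correlation. Because both measures come from the same perimetry test, 0.7 to 0.95 is a reasonable range. If either version is fixed before unmasking, the one-dose error is exactly 0.025.

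**Dilution.** An effect confined to 5 loci becomes 5/k of itself in a k-locus mean: 5/50 = 10%, 5/200 = 2.5%. The values of k are assumed, since no grid size is given. Noise falls too. If locus errors were independent, the standard error would shrink by √(5/k), so the signal-to-noise ratio would be √(5/k) of the regional one: √(5/50) = 0.32, √(5/200) = 0.16. Only if the noise were wholly shared across loci would the loss be the full 5/k. The area may also hold more than 5 loci, and the effect need not stop at its edge. So 5/k is an extreme, not an estimate of lost power.

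**What the current plan runs.** Formal perimetry tests under SAP section 5: none. A by-subject listing is not a test, so none of the error rates above is incurred.

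**The case for a change.** The strongest case for a change starts from the grammar. The synopsis sentence is phrased as a definition of the primary endpoint, not as a gloss on Section 4.1.1, and no visible text says that the two agree. Nothing visible says which area is meant, who sets it or when, and at least 5 loci is only a lower limit. Perimetry data will still be listed, an abbreviated study report will be written, and protocol section 10.1 permits exploratory work outside the SAP. A reader of such work would want to know which measure had been planned, and aligning the wording would cost nothing.

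Part of this stands. The wordings differ, and a tidy protocol would use one. The rest does not lead to a change:

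- The missing definition cannot be held against the plan. Protocol sections 10.2, 10.8 and 10.11, where it would normally sit, are visibly cut in the public copy, and section 8.1 refers assessment detail to manuals that are not available here.
- The report can state the primary endpoint by citing both places in the protocol, and no primary result depends on the choice.
- Section 10.1 requires unplanned analyses not identified in the SAP to be marked as such in the report. The SAP plans no perimetry analysis, so a later unplanned comparison would carry that label whichever loci it averaged. The label does not depend on resolving the two wordings.

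**Conclusion.** The concern does not call for a change. The difference in wording is real, but it is most naturally a short and a long form of one endpoint. The synopsis ties the test to an area set in advance. Inflation would require choosing the measure after seeing results; it would then reach about 0.032 to 0.042 per dose comparison at assumed correlations of 0.95 to 0.7, with 0.05 as the ceiling. Under the SAP now in force the inflation is nil, because no formal test is planned and static perimetry is only listed. Rewording the protocol of a stopped trial would alter no table, listing or conclusion.

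This rests on the abbreviated SAP remaining the governing analysis plan. If formal efficacy testing were reinstated, the set of loci would have to be stated before unmasking.
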